The increasing rate of hospital-acquired infection and sepsis are major causes of morbidity and mortality in intensive care unit (ICU) patients ^{1, 2}. The enormous impact of critical care-related illness demands that we find cost-effective therapies to improve outcome that can be rapidly implemented. Malnutrition is also very common in critically ill patients and is associated with increased hospital-acquired infections and mortality in ICU patients ³⁻¹³. Protein and/or energy deficits are associated with increased rates of hospital infection, skeletal muscle weakness, impaired wound healing, and prolonged convalescence in ICU patients ^{12, 14-17 3, 34-37}. To prevent or treat malnutrition, enteral nutrition EN and/or PN are routinely given worldwide to a significant proportion of ICU patients ³⁻¹³. **Unfortunately, very few well-designed RCTs on the clinical efficacy of specialized nutrition support modalities in critical illness have been performed** ^{18, 19}. Observational studies indicate that initial nutritional goals in ICU settings are infrequently achieved; recent surveys show that both underfeeding, and, to a lesser extent, overfeeding, are common in ICU settings ^{5, 7, 20-22}. Unfortunately, rigorous, prospective studies to determine effects of different energy doses have not been performed ^{5, 7, 12}. The comparative efficacy of energy doses in critically ill patients is thus unknown and clinical recommendations are conflicting and controversial; this issue is the focus of our application. Given the changes in the methods of ICU nutritional support during the past 5-10 years, including tighter blood glucose control ^{23, 24} and the use of overall lower caloric loads than in previous decades (when “hyperalimentation” was the norm), there is a clear need for further CER studies of different modalities of nutrition support based on current ICU clinical care practices ²⁵⁻³¹. Energy (calorie) needs in adult patients in the ICU often vary considerably because of day-to-day changes in clinical conditions ^{9, 32, 33}. However, optimal caloric requirements in critically ill patients are unknown due to a lack of rigorous RCTs. The resting energy expenditure (REE), or basal metabolic rate, is best determined using serial bedside metabolic cart measurements (indirect calorimetry), but technical issues (e.g. air leaks, high inspiratory oxygen concentration) can cause inaccuracies ^{3, 32, 33}. REE can also be estimated using standard equations, most commonly the Harris-Benedict equation (HBE), which incorporates the patient's age, gender, weight, and height ^{3, 10, 12}. Unfortunately, the HBE may over- or underestimate REE in critically ill patients ^{3, 32, 33}.

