- 3) To determine the impact of administered energy dose and energy deficits on global metabolomic patterns, human microbiome, and handgrip strength over time and their association with key clinical outcomes in Aim 1 subjects.

Study Procedures:

A total of 60 subjects will be enrolled in this intent-to-treat trial at Emory University Hospital (EUA) and EUA-Midtown. Patients admitted to either a medical or surgical (non-neurological)

ICU within the previous 168 hours and who are expected to survive and remain in the ICU for at least 96 hours after entry are eligible. Patients enrolled in this study are also those deemed to likely require central venous parenteral nutrition (PN) for 7+ subsequent days after entry on a clinical basis. Patients who meet the following eligibility criteria will be approached:

[figure not shown]
Inclusion criteria: 1) A signed informed consent is in place on the patient's chart; 2) The patient is at least 18 but not more than 90 years of age at time of ICU admission; 3) The patient has a body mass index (BMI) > 40 kg/m²; 4) The patient has been admitted to either a medical or surgical (non-neurological) ICU and is expected to survive and remain in the ICU for at least 72 hours after entry; 5) There is central venous access for administration of the study PN; 6) The patient's primary physician(s) will allow the investigative team to manage the study PN and enteral feedings during the current hospitalization; and 7) The patient is expected to require total or partial central venous PN for 7 or more subsequent days after entry on a clinical basis (e.g. following massive small bowel ± colonic resection, the presence of high output fistulae or perforated small bowel, with demonstrated intolerance to EN or when EN may be contraindicated, as with severe diarrhea or emesis, partial or complete bowel obstruction, severe gastrointestinal bleeding and severe hemodynamic instability, such as with escalating vasopressor requirements).

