Study Schema: Controlled, randomized, double-blind, prospective, parallel-group, intent-to-treat **Aim 1** clinical trial to test the efficacy of three energy doses [0.6, 1.0, and 1.3 x measured REE (MREE), by metabolic cart, respectively], given for 28 consecutive days during the ICU and post-ICU course in critically ill medical and surgical patients requiring parenteral nutrition (PN) ±enteral nutrition (EN) at Emory University. The primary endpoint is total hospital-acquired infections after entry; secondary endpoints are bloodstream infections, ventilator-free days, and ICU and 28-day hospital length of stay and mortality. **Aim 2** examines the effect of cumulative and mean daily measured 28-day energy deficits after entry on Aim 1 clinical outcome endpoints and relationships between estimated REE (Harris-Benedict equation) at study entry. **Aim 3** explores the impact of energy dose and cumulative and mean daily 28-day energy deficits on global metabolomic patterns, microbiome, and strength over time and in association with key clinical outcomes in Aim 1.

↑ Plasma (metabolome), microbiome, and strength analysis

Data Collection: Baseline data collected will include APACHE II score, and clinical and demographic data. The following will be collected during the course of the study:

A) Measured resting energy expenditure (MREE; per metabolic cart) will be determined on the baseline day before 2 pm. The goal energy dose composition of PN for all three energy doses for each enrolled subject is calculated by the blinded research team members. The metabolic cart-derived REE will be used to determine basal energy expenditure (REE) and thus the initial energy dosing^{5, 10, 12}. MREE will be determined at baseline and 5x weekly (M-F before 2 pm; see Aim 2) using a state-of-the-art metabolic

cart and standard methodologies by a study team respiratory technician with prior experience and expertise in clinical indirect calorimetry. In the event that the metabolic cart is not available, the most recent measurements will be used. The nutrition will not be adjusted if the MREE is <10% changed from the reading the day before.

- B) Longitudinal SOFA scores of organ dysfunction/failure: Sequential organ failure assessment (SOFA) scores will be calculated in the morning of each ICU day ⁶⁰. The baseline Apache II score on the day of ICU admission will also be calculated in all patients.

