standardized CRFs. The primary endpoint is total nosocomial infection rate during the 28-day study period. Secondary Aim 1 post-entry endpoints to be monitored include: 1) 28-day hospital mortality; 2) Rate of new nosocomial blood stream infections (BSIs) during the initial 28 days; 3) Rate of new nosocomial infections during the initial 28 days; 4) mean ICU SOFA score; 5) ICU ventilator-free days at day 28; 6) ICU and total hospital length of stay.

Hospital nutrition support - Administration of double blind parenteral and enteral nutrition:

Briefly, the nutritional goals are to provide total daily calorie (kcal) intake [from PN + dextrose-containing IV fluids (> 500 mL/day) + propofol/clevidipine + any enteral feedings) at 0.6, 1.0 or 1.3 x baseline MEE (per metabolic cart). We will then serially adjust total PN/EN energy dosing based on real-time serial cart REE measurements during the ICU stay, as indicated by the energy dose group to which the patient is randomized. The total amino acid/protein intake goal is 1.2 g/kg/day. Dextrose will initially comprise 70% of PN non-amino acid kcal and IV fat (30% Intralipid[®]) 30% of PN non-amino acid kcal daily, adjusted as clinically indicated. The 1.0 x REE energy dose study group will serve as the control group in this CER study. Study PN will be continued only if deemed indicated by the investigators and the primary physicians. Daily intake of study PN volume (mL), PN dextrose (g), PN lipid emulsion (g), intake of study tube feeding volume, and daily PN and enteral (oral or tube feeding) volumes will be calculated and entered into the CRFs daily for the initial 28 days after entry, beginning on day 1.

Study subjects will receive a maximum of 28 days of double blind study PN ± EN. Subjects will be transitioned from PN to enteral feeds as soon as tolerated and clinically indicated. Study PN will be discontinued when enteral intake of \geq 50% of energy requirements is achieved for \geq 48 hr. The amount of PN administered will be decreased as a function of actual enteral nutrient intake to maintain daily goals. The 24-hr daily study PN will be prepared under sterile laminar air flow hood conditions by the unblinded research pharmacist and pharmacy technician at each site. The study EN will be made in the Metabolic Kitchen or in the compounding area of the pharmacy.

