Determination of energy deficit: Energy intake from PN \pm EN (tube feeds + any oral diet) will be determined as outlined in Aim 1 each day for the initial 28-days of study. MREE will be determined by metabolic cart 5x week (Monday through Friday) before 2 pm. Any PN or EN being administered will be continued uninterrupted during MREE determinations. The 5 daily cart measurement results (kcal/day) for each study week will be averaged and that mean daily value used as the daily measured energy requirement for all 7 days of that week. The daily energy deficit will be calculated by subtracting the calculated mean daily MREE during each study week from the actual daily energy intake. The cumulative and mean daily ICU and 28-day energy deficits will be determined. Metabolic cart measurements will not be performed on any given day in patients whom are in isolation due to resistant microorganism infection (contraindicated), or if the patient requires a fraction of inspired oxygen of < 60%, has a requirement for positive end-expiratory pressure of > 12 cm H₂O, or has a documented leak in the ventilator or chest tube systems (precluding accurate cart measurements) ^{32, 33}. The estimated REE by the HBE(outlined in detail in Table 3 of reference 3 ⁶¹) will be calculated on the baseline day using most recent available pre-ICU dry body weight.

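### The 10% no-adjustment rule compares each MREE with the previous day's reading rather than with the MREE behind the current dose, so smaller same-direction changes can accumulate between resets.

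*Combined protocol and SAP*

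**What the plan says.** The no-adjustment rule is in Data Collection, item A: "The nutrition will not be adjusted if the MREE is <10% changed from the reading the day before". The same item schedules cart readings at baseline and then Monday to Friday. It also provides a fallback: "In the event that the metabolic cart is not available, the most recent measurements will be used".

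The section on hospital nutrition support sets the starting dose from the baseline measurement and gives the general intention: "We will then serially adjust total PN/EN energy dosing based on real-time serial cart REE measurements during the ICU stay". It names no threshold, reference value or cumulative check.

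The section on determination of energy deficit averages the week's readings, but only to compute the deficit, by "subtracting the calculated mean daily MREE during each study week from the actual daily energy intake". That average does not feed back into the dose. The section also lists reasons for skipping a reading, for example: "Metabolic cart measurements will not be performed on any given day in patients whom are in isolation due to resistant microorganism infection".

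**The concern.** A tolerance band should keep the dose close to its target. This one limits the change between two successive readings and leaves the gap between the current reading and the dose-setting reading unlimited. A 10% rise in one day permits an adjustment; the same rise spread over two days does not. No other section closes the gap.

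The assigned multiple of measured REE is the treatment in this trial, and the Background expects REE to move: "Energy (calorie) needs in adult patients in the ICU often vary considerably because of day-to-day changes in clinical conditions". What is at stake is how closely each patient's prescription follows the assigned multiple, that is, the spread of prescribed dose within an arm. Arm means change little unless REE trends.

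The rule is also undefined on Mondays and after a skipped reading, when there is no reading from the day before.

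**Working it through.** The plan has no figure of its own to reproduce here.

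**Inputs from the protocol.** Tolerance 10%, comparator the previous day's reading, and Monday-to-Friday schedule (Data Collection, item A); multiples 0.6, 1.0 and 1.3 (hospital nutrition support). A Monday-to-Friday week gives four day-before comparisons, Tuesday to Friday.

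**Assumptions.** The size and pattern of REE change are not in the documents. A change of 10% or more is taken to reset the dose to the current reading.

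**Constructed path.** After k equal changes of g, each under 10%, MREE is (1+g)^k times the dose-setting value, and the prescribed multiple is the assigned one divided by (1+g)^k.
- Two rises of 5%: 1.05^2 = 1.1025, already over 10%, with no adjustment.
- Four rises of 5%: 1.05^4 = 1.2155. The 1.0 arm is at 1/1.2155 = 0.82 and the 1.3 arm at 1.3/1.2155 = 1.07 times current MREE.

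**Bound with the dose-setting MREE as comparator.** If no change is triggered, current MREE lies between 0.90 and 1.10 of the dose-setting value. The prescribed multiple is then between 1/1.10 = 0.91 and 1/0.90 = 1.11 of the assigned one. For the 1.3 arm that is 1.3 × 0.91 = 1.18 to 1.3 × 1.11 = 1.44.

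**Frequency.** Simulation of at least 200,000 patients per setting. The ratio is dose-setting MREE divided by current MREE, and a patient is off target if the average ratio differs from 1 by more than 0.10. REE either follows a random walk with normal daily proportional changes or scatters normally around a fixed mean. The Monday rule is taken both ways; for the Monday reset, the enrolment weekday is uniform over Monday to Friday. Last digits vary by 0.1-0.2 between runs.

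Share of patients off target under the rule as written, at SD 3% / 5% / 7%:

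| Assumption | 4 readings | 5 readings | 10 readings |
|---|---|---|---|
| Random walk, Friday carried forward | 1.6 / 8.6 / 8.5% | 2.5 / 10.6 / 9.5% | 9 / 19 / 12% |
| Random walk, Monday re-doses | 0.3 / 2.1 / 2.5% | 0.1 / 1.4 / 1.7% | 0.0 / 0.2 / 0.2% |
| Stable mean, Friday carried forward | 0.1 / 1.6 / 2.4% | 0.1 / 1.5 / 2.1% | 0.1 / 1.0 / 1.2% |

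With the dose-setting comparator the share is at most 0.01% in these settings. The random-walk share does not keep rising with SD because larger steps trigger more resets.

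- **Reading-days more than 10% off** (random walk, SD 5%, 10 readings): about 25% with Friday carried forward and 9% with a Monday reset, against about 2% with the corrected comparator. The residue is the 1.11 edge of the bound.
- **Between-patient SD of the 10-reading average ratio** (random walk, SD 3/5/7%): 5.9/7.7/6.5% with Friday carried forward and 2.1/3.0/2.9% with a Monday reset, against 2.9/2.3/2.0% with the corrected comparator.
- **Trend of +1% per reading**, mean ratio at the 10th reading: 0.92/0.96/0.99 with Friday carried forward, 0.98/0.99/1.00 with a Monday reset.
- **Trend of -1% per reading**: 1.11/1.08/1.03 with Friday carried forward, 1.02/1.02/1.01 with a Monday reset.

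**The case against.** The strongest objection is the weekly break. Taken strictly, the exception cannot apply on a Monday, because Sunday has no reading. The general intention to adjust serially then governs, and Monday's reading resets the dose. The carry-forward sentence concerns an unavailable cart, not an unscheduled weekend. On that reading drift is confined to at most four comparisons, and the 10-reading shares nearly vanish. At SD 3% the plan's between-patient spread (2.1%) is even tighter than under the fix (2.9%). This stands as a limit on size: the documents do not settle the Monday comparator, so both readings must be shown. It does not remove the defect within the week, since about 9% of reading-days are still more than 10% off at SD 5%.

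Second, the larger percentages need a random walk, which no section supports; day-to-day variation in need fits fluctuation around a stable mean equally well. This also stands, and the two-step arithmetic does not depend on it.

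Third, a threshold that avoids order changes for small variation is a legitimate choice, this is a 60-patient pilot, and the Aim 2 deficit records departures from need. All true, but the objection here is to the comparator, not to having a threshold, and recording a departure does not correct it.

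**Conclusion.** The rule is wrong as written in its comparator only, and the severity is modest. Same-direction changes below 10% can accumulate between resets past the plan's own tolerance. That follows from the wording alone. How often it matters rests on assumed REE variability and an unstated Monday rule. Off-target shares run from essentially none to about 19% of patients, and are 0-2% if REE is stable.

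Serial adjustment is stated for the ICU stay, and the inclusion criteria require only that the patient "is expected to survive and remain in the ICU for at least 72 hours after entry" (the opening of Study Procedures says 96 hours). The 4- and 5-reading figures therefore fit shorter stays better than the 10-reading ones.

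A reader might infer more than this:
- **That drift is permanent, or that the 1.3 arm slides into the 1.0 arm.** That takes a sustained one-way run with no single change of 10% or more and, across weeks, no Monday reset. With a Monday reset, even a steady 1% trend leaves the mean ratio at the 10th reading within about 2% of target.
- **That the infection comparison is biased or loses power.** The documents give nothing from which to derive an effect on the infection endpoint, power or type I error, and none is claimed.

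**What to change.** Reword the sentence in Data Collection, item A along these lines: *Leave the prescription unchanged when the new MREE differs by less than 10% from the MREE on which the current dose was based; apply the same comparison on Mondays and at the first reading after any missed day.*

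At each reading this keeps the prescribed multiple within 0.91-1.11 of the assigned one and settles the Monday question. It does not bound actual intake, or the dose on days without a reading.

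The cost is one sentence and possibly more PN order changes. For a random walk over 10 readings, mean changes per patient at SD 3%, 5% and 7% go from 0.01 to 0.50, 0.45 to 1.33 and 1.53 to 2.25 if Friday would have been carried forward: at most about 0.9 extra. Around a stable mean there is essentially no difference (1.58 against 1.56 at SD 5%).

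If Mondays would otherwise always re-dose, the fix means fewer changes. Ten weekday readings contain two Mondays, and the other eight trigger at the as-written rate: 2 + 0.8 × 0.45 = 2.4 at SD 5%, against 1.33.

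The gain is smaller if the scatter is pure measurement noise. With Friday carried forward, patients more than 10% off their true mean at the 10th reading fall only from 8.5% to 4.6% (SD 5%) and from 21% to 15% (SD 7%).

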Twenty-eight day mortality will be summarized as a proportion plus the 95% confidence interval (overall and for each treatment group). The 28-day mortality will be compared between treatment groups using a chi-square or Fisher's exact test. The potential association of each of the categorical prognostic factors (gender, race, high or low Apache score, clinical center) with mortality will also be evaluated using a Chi-square test or Fisher's exact test. Baseline continuous prognostic factors (age, SOFA score, blood glucose) will be compared by treatment group using the Wilcoxon rank-sum test. Odds ratios will be calculated to measure the degree of association. All statistical tests will be 2-sided. Factors significant to at least a value of $P \leq 0.20$ in the univariable analyses will be used in multivariable logistic regression analyses. Forward and backward stepwise selection will be used if necessary to choose prognostic variables for a multivariable logistic regression model. The odds ratio and its 95% confidence interval will be calculated for each factor in the presence of others in the final model.

Days on mechanical ventilation, length of ICU stay and hospital length of stay will be summarized with percentiles (25th, 50th and 75th) and the median absolute deviation. These secondary outcomes will be compared between the 3 treatment groups using the Kruskal-Wallis test. Repeated-measures analyses of daily SOFA scores and laboratory measures such as blood glucose will be analyzed with a means model with SAS Proc Mixed (version 9, mixed linear models) providing separate estimates of the means by time on study (days 0, 3, 7, 14, 21, and 28) and treatment group (energy dose: 0.6, 1.0 and 1.3 x REE). An unstructured variance-covariance form among the repeated measurements will be assumed for each outcome and estimates of the standard errors of parameters will be used to perform statistical tests and construct 95% confidence intervals. T-tests will be used to compare the pairwise differences between the model-based treatment means (least-squares means) at each time point. Statistical tests will be 2-sided. The model-based means are unbiased with unbalanced and missing data, so long as the missing data are non-informative (missing at random). A dropout process is assumed to be missing at random if; conditional on the observed data, the dropout is independent of the unobserved measurements.

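### The listed SOFA endpoint is the mean over the ICU stay, but the only planned between-arm comparison is of model means at fixed days to day 28, which does not test it and extrapolates past death and ICU discharge

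*Combined protocol and SAP*

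**What the plan says.** Three places in the combined protocol and SAP bear on this.

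- **Endpoint.** The section on serial data entry via case report forms lists, among the secondary Aim 1 endpoints, "4) mean ICU SOFA score; 5) ICU ventilator-free days at day 28". The fourth of these, "mean ICU SOFA score", is one summary per patient over the ICU stay.
- **Collection.** Data Collection, item B, says that SOFA "scores will be calculated in the morning of each ICU day". Patients are followed on the ward afterwards, but no section provides for a SOFA score outside the ICU.
- **Analysis.** Statistical Analysis, For Aim 1, says: "Repeated-measures analyses of daily SOFA scores and laboratory measures such as blood glucose will be analyzed with a means model". The model gives a separate mean for each arm at days 0, 3, 7, 14, 21 and 28. On covariance: "An unstructured variance-covariance form among the repeated measurements will be assumed for each outcome". T-tests then "compare the pairwise differences between the model-based treatment means (least-squares means) at each time point". On missing data: "The model-based means are unbiased with unbalanced and missing data, so long as the missing data are non-informative (missing at random". The section defines missing at random in general terms and mentions neither death nor ICU discharge.

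The Kruskal-Wallis test in the same section covers ventilation days, ICU stay and hospital stay, but not SOFA. The general opening of the Statistical Analysis section provides descriptive summaries of continuous variables.

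**The concern.** An analyst who follows the plan will report up to six sets of pairwise SOFA comparisons, none of which is the listed endpoint. The average over a patient's ICU days and the arm mean on a fixed calendar day are different quantities, and an energy dose that changes time to discharge or death can move them differently.

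The later fixed days raise a second problem. A patient who has left the ICU contributes no score, so the day-21 and day-28 means combine the few scores available with what the model implies for everyone else. For a discharged patient that is an extrapolation. For a patient who has died there is no SOFA value to estimate, whatever is assumed about missingness. Discharge tends to follow low SOFA and death tends to follow high SOFA, so the patients who remain are a selected group.

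The Abstract says that the pilot exists to inform later Phase III trials. A late SOFA contrast resting on a handful of patients could be carried into that planning as if it described the whole arm.

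**Working it through.** The documents state no SOFA mean, standard deviation, effect size or power, so there is no figure to reproduce.

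**1. Endpoint against analysis**

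| Item | Listed endpoint | Planned comparison |
|---|---|---|
| Unit | One mean per patient | One model mean per arm and day |
| Period | That patient's ICU days | Fixed days 0 to 28 |
| After ICU exit | Nothing needed | Implied by the model |
| Test between arms | None given | Pairwise t-tests at each day |

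**2. Which scores enter the model**

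The text speaks of daily SOFA scores but lists six days, which are also the metabolomics blood-draw days. The two readings differ.

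- *Six days only:* 3 arms × 6 days = 18 means, and 6 × 7 / 2 = 21 covariance parameters, from 60 patients.
- *All days 0 to 28, unstructured:* 29 × 30 / 2 = 435 covariance parameters from 60 patients, which is not workable.

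The six-day reading is therefore the practical one. Under it, a patient who leaves on day 13 is represented by the scores at days 0, 3 and 7. The morning scores from days 8 to 13 are recorded but not conditioned on, although they are the ones most closely tied to exit. Missing at random given the six-day data is then doubtful for SOFA.

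**3. How many patients support the late means**

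Inputs: 20 patients per arm and three arms (Abstract). Assumption: time to ICU exit, by discharge or death, is exponential with median m days. The documents give only a minimum expected stay (72 hours in the inclusion criteria, 96 hours in the paragraph before them).

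Proportion still in the ICU at day t: p = 2^(−t/m). Expected number per arm: 20p. Chance that at least one of three arms is empty: 1 − [1 − (1 − p)^20]^3.

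| Median m (days) | Day 14, per arm | Day 28, p | Day 28, per arm | At least one arm empty at day 28 |
|---|---|---|---|---|
| 7 | 5.0 | 0.0625 | 1.25 (about 1.2) | 62% |
| 10 | 7.6 | 0.144 | 2.9 | 13% |
| 14 | 10.0 | 0.25 | 5.0 | 1% |
| 21 | 12.6 | 0.397 | 7.9 | about 0.01% |

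For m = 7: (1 − 0.0625)^20 = 0.275, and 1 − (1 − 0.275)^3 = 0.62. The chance that at least one arm has one patient or none at day 28 is 95%, 48% and 7% for medians of 7, 10 and 14 days. If an arm is empty, its day-28 mean cannot be estimated and the planned t-tests involving it cannot be done.

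**4. Do the two quantities agree?**

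A simulation with 4,000 patients per arm gave both arms the same SOFA process and changed only the exits. All parameters were assumed: starting SOFA mean 8 and SD 2.5, mean slope −0.15 per day, death likelier at high SOFA and discharge likelier at low SOFA.

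- Higher death hazard in one arm (deaths 35% against 14%): mean ICU SOFA differed by 7.04 − 6.76 = +0.28, and the six-day model's day-28 mean by 4.33 − 4.47 = −0.14. The signs are opposite.
- Faster discharge in one arm: mean ICU SOFA differed by 7.18 − 6.74 = +0.44.

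This run left out the exit-day score. A rerun that kept it gave the same signs and somewhat smaller differences in mean ICU SOFA. The figures show only that the two quantities can part, and that mean ICU SOFA is itself sensitive to exit. They do not estimate bias in this trial.

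**The case against.** The strongest reply is that SOFA is scored every ICU morning, so the score on the day of exit is normally on record before a discharge and before most deaths. Exit can then depend on observed data, which is what missing at random allows. A reader might infer that the score driving exit goes unseen, so that missing at random must fail. The collection schedule does not support that inference. The doubt is narrower: it arises if only the six listed days enter the model. A model using all daily scores under a simpler covariance structure would meet much of it, but the plan specifies an unstructured form. Nor would such a model give meaning to a SOFA value after death, or test the listed endpoint.

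Two other strong readings should also be resisted. The plan does not assert that its SOFA means are unbiased; its statement is conditional and covers all repeated outcomes. Nor is the endpoint left without any analysis, since descriptive summaries are provided for. What is missing is a between-arm comparison.

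It is also fair to say that mean ICU SOFA is cut short by the same exits. Section 4 of the working shows that faster discharge alone can make an arm look worse. That objection stands and has to be disclosed with the fix.

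Finally, this is one of six listed secondary endpoints in a pilot, and the Study Schema leaves SOFA out of its own list. That limits the stakes.

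**Conclusion.** The point holds. The planned SOFA comparison does not test the endpoint that the protocol lists, and its late-day means rest on the patients still in the ICU plus extrapolation to those discharged or dead.

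How thin the late data will be depends on an ICU-stay distribution that the documents do not give. Under exponential stays with medians from 7 to 21 days, between about 1.2 and 7.9 patients per arm remain at day 28. An empty arm is likely at the short end of that range and negligible at the long end.

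A reader might want a bias in SOFA points. The documents do not support one: they give no SOFA distribution and no exit rates, and any such figure would be measured against an imagined SOFA course that continues after death.

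The consequence is confined to interpreting SOFA. The primary endpoint is not affected. This is a cheap improvement, not a condition for the trial to proceed.

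**What to change.** In the SAP text for Aim 1:

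1. Define the endpoint as each patient's mean SOFA over ICU days within the 28-day period. Compare it between arms with adjustment for baseline SOFA and the randomisation strata (APACHE II group and hospital).
2. Limit mixed-model inference on SOFA to the early days (0, 3 and 7). Present days 14, 21 and 28 descriptively, with the number still in the ICU shown for each arm.
3. State that the missing-at-random justification does not cover SOFA after death or ICU discharge, and say which morning scores enter the model.
4. Add one rank-based sensitivity analysis in which patients who die are ranked worst.
5. Report mean ICU SOFA beside ICU length of stay and mortality, and say why: faster discharge or earlier death can shift it even when the SOFA process is the same. The ranking in item 4 deals with death but not with discharge.

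The cost is SAP wording and one extra analysis, on data already being collected. The price is that the late SOFA time course becomes descriptive and that the endpoint cannot be read alone.
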